## **7.3 Center Pooling**

Since the study was terminated early, no assessment of poolability of data across centers will be performed.

## 7.4 Handling of Missing, Unused, and Spurious Data and Dropouts

Since the impact of missing data is expected to be small, and only descriptive statistics will be applied no multiple imputation method for missing data is planned. For subjects who are lost to follow-up, the time to event will be censored at the last available contact date.

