### 7.1 Study Subjects

#### 7.1.1 Disposition of Subjects

The number of patients assessed for eligibility, enrolled, randomized, number of patients with follow-up visits completed and the number of patients with device data interrogation available will be summarized by table and by flow-chart.

The reason for study exit will be presented in table.

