### 7.1.3 Analysis Sets

The following analysis sets were defined in the CIP:

- The Per Protocol Analysis Set (PP) includes all patients actively enrolled in the study, who signed Informed Consent Form (ICF), fulfilled the inclusion/exclusion criteria and that have one day in Sinus Rhythm at the time of enrollment or after the enrollment.
- The Intention-to-Treat Set (ITT) includes all patients actively enrolled in the study, who signed ICF, and fulfilled the inclusion/exclusion criteria.

Since the study was terminated early with low number of patients enrolled, no significant differences in terms of sample size between the PP and ITT population sets are expected. Moreover, the device data interrogation compliance, due to the COVID-19 pandemic, was far from what expected in the investigation plan. For these reasons the Full Analysis Set (FAS) including all patients randomized into the study and fulfilling the inclusion/exclusion criteria will be used throughout the analysis.

The primary endpoint and the secondary endpoints will be analyzed in the FAS population with descriptive statistics without testing formal hypotheses. For the same reason no analyses on subsets of the FAS as outlined in the study protocol will be performed. In addition, individual subject listings could be generated, if needed.

The randomization arm will be used throughout the analysis.

Information about, patients assigned to the different treatment arm then the arm to which the patient was randomized (i.e. wrong device programming in terms rATP feature), will be reported in the protocol deviation table or listing if needed.

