### **7.2.2 Derived Variables**

Variables to evaluate the primary endpoint, as well as daily AF burden metrics, number of successful and unsuccessful treated AT/AF episodes out of detected episodes, number of delivered therapies per episode, and number of ATP sequences will be derived from the device datasets and will be described in detail in the SPR (ref).

The exposure time (months) for the time to first persistent AF will be computed from the date of randomization to the date of the last device save to disc for patients without persistent AF recurrence or to the date of first recurrence of persistent AF recurrence otherwise  $[(\text{data end} - \text{data in})/30.4]$ .

Variables to evaluate secondary endpoints as all-cause death, cardiovascular hospitalization (HF, AF or other), stroke, TIA or other thromboembolic events and annual rate for all-cause hospitalization will be derived from the adverse event dataset and will be described in detail in the SPR (ref).

The exposure time (months) for the secondary endpoints will be computed from the date of randomization to the date of the notice (follow-up visit or adverse event) for patients without events or to the date of the specific event otherwise  $[(\text{data end} - \text{data in})/30.4]$ .

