## 7.9 Evaluation of Objectives

Endpoints defined in the section 4.2 will be used to evaluate objectives.

A device data quality analysis will be performed before the derivation of the analysis variables. Endpoints based on device data could be biased by the not compliance of the device data interrogation process compared to the clinical investigation plan.

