## 7.12 Changes to Planned Analysis

The original analysis described in CIP assumed that the study would recruit 758 patients and formal hypotheses would be tested. Due to early termination of the study, the formal hypothesis testing will not be conducted in the analysis and only descriptive statistics and figures will be presented. A final decision on the study endpoints evaluation will be taken only when the complete set of clinical and device data will be collected and evaluate in terms of quality and reliability.

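### SAP 7.4 assumes a small missing-data impact that SAP 7.1.3 and 7.9 contradict; no sensitivity analysis is planned, and two sections give different censoring dates for the primary endpoint

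*SAP*

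**What the plan says.** On missing data, SAP 7.4 reads: "Since the impact of missing data is expected to be small, and only descriptive statistics will be applied no multiple imputation method". It then adds a censoring rule: "For subjects who are lost to follow-up, the time to event will be censored at the last available contact date".

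Other SAP sections bear on the same data:

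- 7.1.3, explaining the choice of the full analysis set: "the device data interrogation compliance, due to the COVID-19 pandemic, was far from what expected in the investigation plan".
- 7.9, before the endpoint analyses: "Endpoints based on device data could be biased by the not compliance of the device data interrogation process". It also says: "A device data quality analysis will be performed before the derivation of the analysis variables".
- 7.2.2 derives the primary endpoint from the device datasets and runs exposure from randomisation "to the date of the last device save to disc for patients without persistent AF recurrence".
- 7.1.1: "the number of patients with device data interrogation available will be summarized by table and by flow-chart".
- 7.12: "A final decision on the study endpoints evaluation will be taken only when the complete set of clinical and device data will be collected", with a review of quality and reliability.
- 7.2.1 and 7.9.1 plan Kaplan-Meier curves and survival probabilities with 95% intervals by arm, if numbers are adequate. There is no test and no hazard ratio.

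Protocol 13.2.5 contains almost the same small-impact sentence. It also provides for imputing missing values by a suitable method and rerunning the analysis.

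**The concern.** The reason given in 7.4 does not fit what the same document reports. The premise was already in the February 2019 protocol. The SAP is dated 27 August 2021, after the final visits set for June and July 2021, and it describes poor interrogation compliance in the past tense. The protocol's provision to impute and rerun is not carried forward, and SAP 7.12 does not list its removal.

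What is at stake is how the primary estimate can be read. A Kaplan-Meier curve censored at the last device read uses each patient's observed time. It is unbiased only if the end of device observation is unrelated to the risk of persistent AF. The SAP neither states that assumption nor plans to test it. It also does not say how it treats a patient with no device read after randomisation. Under 7.2.2 such a patient has no exposure time, yet still counts in the full analysis set. The printed intervals would not show any of this.

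A second problem is the censoring date. The rules in 7.4 and 7.2.2 can give different dates for the same patient, and the choice changes the estimate.

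**Working it through.** **Figures in the plan.** The plan gives no figure for interrogation coverage, so there is none to reproduce on this point. The planned sample size is not in dispute. HR = ln(0.775)/ln(0.85) = 1.568 needs 156 events (Schoenfeld) or 161 (Freedman). With a mean event probability of 0.247 (18-month uniform accrual, 24-month minimum follow-up), N is 632 or 652. Dividing by 0.85 gives 744 or 768, within 3% of 758.

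**Inputs from the documents.** Arms of 37 (interventional) and 38 (control), SAP 6. Control survival of 85% at 24 months, hence 15% incidence, SAP 6. Assumed loss to follow-up of 15%, SAP 6. The share of patients without device data is *assumed* throughout.

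**1. Bounds for one arm.** With n patients, m unobserved and x events among the observed, crude incidence lies between x/n and (x + m)/n. The width is m/n.

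- m = 6, x = 5 of 31: 5/37 = 13.5% to 11/37 = 29.7%.
- m = 11, x = 4 of 26: 4/37 = 10.8% to 15/37 = 40.5%.

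**2. Bounds for the difference between arms** (interventional minus control), with 15% incidence among observed patients in both arms:

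| Assumed unobserved | Counts (int., control) | Lower | Upper |
|---|---|---|---|
| 10% | 4, 4 | -10.6 points | +10.8 points |
| 20% | 7, 8 | -20.7 | +19.2 |
| 30% | 11, 11 | -29.1 | +29.6 |
| 50% | 18, 19 | -49.8 | +48.9 |

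First row, upper bound: (0.15 × 33 + 4)/37 - (0.15 × 34)/38 = 0.242 - 0.134 = 0.108. With three unobserved per arm, the upper bound is (0.15 × 34 + 3)/37 - (0.15 × 35)/38 = 0.219 - 0.138 = +8.1 points. At 15%, the expected events over a full 24 months are only 0.15 × 37 = 5.6 and 0.15 × 38 = 5.7, so a few unobserved patients carry weight.

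**3. Effect of the censoring date.** Assume a constant hazard with 15% incidence at 24 months, so survival to month 12 is √0.85 = 0.922. Let a fraction f have device data that stop at month 12 but contact to month 24. If those who are event-free are censored at contact, the curve reads

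S(24) = 0.922 × [f + (1 - f) × 0.922].

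- f = 0.15 (the design loss rate): 0.922 × 0.934 = 0.861, incidence 13.9%.
- f = 0.5: 0.922 × 0.961 = 0.886, incidence 11.4%.
- f = 1: 0.922, incidence 7.8%.

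If device data stop at month 18 for everyone, the reading is 1 - 0.85^0.75 = 11.5%. The true value is 15% in each case. Contact-date censoring keeps patients in the risk set when no device event could be seen, so under this model it lowers the estimate.

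**The case against.** The strongest reply is that the analysis is descriptive. That is the second reason in 7.4 and it stands on its own: no test, hazard ratio or non-inferiority conclusion depends on the missing data. This limits the consequence. It does not remove bias from an estimate printed with a 95% interval.

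The SAP also has safeguards. A reader might infer that it does nothing about missing data, and that would be wrong: it has censoring rules, an availability count, a device data quality review and a deferred decision on the endpoints. However, the count does not show how much follow-up is covered, and neither the review nor the decision has a stated criterion or a planned sensitivity result.

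Four other stronger readings are not supported:

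- *That the primary result is a complete-case result.* Partly followed patients contribute until censored. Only those with no read after randomisation contribute no time, and the documents do not say that any exist.
- *That every missed visit lost data.* Devices store episodes that a later read retrieves (Protocol 9.1.2 and 9.6), and a closing visit was scheduled. Permanent AF is a physician's decision (Protocol 9.6) and does not depend on a download alone.
- *That symptomatic patients were interrogated more often.* This is plausible, and investigators know the arm, but no section says it happened.
- *That the one-arm ranges can be set against the 7.5-point margin.* The margin is a between-arm difference that the SAP no longer tests.

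The derivation details are in a separate programming document that was not available for this review. It may settle the censoring date, but the SAP text would still need to agree with it.

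**Conclusion.** The concern holds in a limited form. The small-impact premise in SAP 7.4 is contradicted by 7.1.3 and 7.9. The primary estimate relies on unstated non-informative censoring, its intervals cover sampling error only, and no sensitivity analysis is planned. Sections 7.4 and 7.2.2 also disagree on the censoring date.

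The size and direction of any bias cannot be known from the documents. The bounds rest on assumed missing shares: between arms they run from about ±11 points at 10% unobserved to about ±49 at 50%. They are worst-case limits, not expected errors. The 7.8% reading rests on a constant hazard and on every patient's device data stopping at month 12. At the design loss rate of 15%, the same model gives 13.9%. For a descriptive report on 75 patients this is a correction that should be made, but it does not invalidate the study.

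**What to change.** 1. Delete the small-impact premise from 7.4. The descriptive purpose can remain as the reason for not imputing.
2. For the device-derived primary endpoint, censor at the last save to disc in both 7.2.2 and 7.4.
3. State in 7.9.1 that the estimate assumes non-informative censoring, and say how patients with no device data after randomisation are handled.
4. Report by arm the number of such patients and the share of randomisation-to-exit time covered by device data. The count extends the 7.1.1 summary; the coverage share is new.
5. Add to 7.9.1, as a sensitivity result, best-case and worst-case bounds on primary incidence by arm. Patients with no post-randomisation device data and no recorded permanent AF are counted first as all event-free, then as all events. Crude proportions avoid inventing event dates. These bounds do not address partly covered patients, for whom the coverage share is the guide.

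Do not restrict the analysis to in-window or remote reads. Protocol 9.10 asks sites to collect late data as near the due date as possible, and late and closing reads recover stored episodes. Excluding them would increase the missing data.

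The cost is SAP wording, a few small tables from data already collected, and visibly wider stated uncertainty. Database lock was set for 1 September 2021, so later changes would be reported as SAP deviations in the study report, as 7.2.1 provides.

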13.2.9. Evaluation of objectives

Time to event analysis will be performed by means of the Kaplan Meier method. Time to event must be calculated as time from enrollment date or the first day in sinus rhythm after enrollment, to the date of event for patients with complications, and time from enrollment date to the last patient information date otherwise (the date of last transmission, date of last follow-up, exit or death date). Difference in time-dependent event between population subgroups will be evaluated using a Cox proportional hazard regression model. The proportionality of the risk will be tested with the Schoenfeld method. Confounding factors will be identified among baseline characteristics and device data eventually collected before inclusion. All outcomes will be evaluated considering confounding factors by means multivariate models or stratification as appropriate. Rates were computed for 100-person years and were compared by means of the Poisson model using the scale deviation parameter to adjust for over-dispersion. Incidence rate ratios (IRRs) with their 95% confidence intervals (CIs) were computed to measure events reductions in the interventional arm. IRRs were also adjusted to account for the effect of potential confounders.

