#### 4.2.2 Secondary Endpoints

1. To compare the two atrial ATP Programming arms in terms of clinical endpoints reported below:
  - all-cause death (at the end of 24 months), measured as time to event;
  - cardiovascular hospitalization (HF, AF or other), measured as time to first event and annual rate;
  - Annual rate for all-cause hospitalization;

- AT/AF burden metrics, measured in terms of time to first event (daily burden  $\geq 1$  day,  $\geq 2$  days,  $\geq 30$  days) or the ratio between time in AT/AF and the observation period;
  - number of successful and unsuccessful treated AT/AF episodes out of detected episodes;
  - number of delivered therapies per episode;
  - number of ATP sequences;
  - stroke, TIA or other thromboembolic events;
  - LA diameter (where available);
  - percentage of patients treated by anticoagulation therapy according management guideline;
  - electrical or pharmacological cardioversions, measured as time to first event and annual rate;
  - biventricular pacing percentage (in CRT-P /CRT-D patients).
2. Composite endpoint made of death, cardiovascular hospitalizations, stroke, TIA or other thromboembolic events;
  3. To evaluate the incidence of persistent AF in patients with sick sinus syndrome compared to the one found in the Minerva trial, and characterize the difference between the European and Indian populations;
  4. To evaluate the efficacy of atrial ATP therapies as a function of the device type (IPG, ICD, CRT-D, CRT-P), and population characteristics (baseline characteristics, implant indications).

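### SAP 7.4 and SAP 7.2.2 give lost-to-follow-up patients two different censoring dates for device-detected AF, and the protocol and SAP text does not say which applies

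*SAP*

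**What the plan says.** The SAP contains two censoring rules that meet in the same patients.

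- **By endpoint (SAP 7.2.2).** Persistent-AF exposure runs from randomization "to the date of the last device save to disc for patients without persistent AF recurrence". Patients lost to follow-up are not excepted.
- **By type of patient (SAP 7.4).** "For subjects who are lost to follow-up, the time to event will be censored at the last available contact date". No endpoint is excepted. Protocol 13.2.5 has the same sentence.

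Two further rules bear on the point.

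- **Secondary endpoints (SAP 7.2.2).** "The exposure time (months) for the secondary endpoints will be computed from the date of randomization to the date of the notice", meaning a visit or an adverse event. SAP 4.2.2 lists among the secondary endpoints "AT/AF burden metrics, measured in terms of time to first event", and 7.2.2 derives burden from the device datasets.
- **Protocol 13.2.9.** Patients without an event contribute "time from enrollment date to the last patient information date otherwise (the date of last transmission, date of last follow-up, exit or death date"). The four dates are not ranked.

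On data coverage, SAP 7.1.3 reports that "the device data interrogation compliance, due to the COVID-19 pandemic, was far from what expected in the investigation plan", and SAP 7.9 warns that "Endpoints based on device data could be biased by the not compliance of the device data interrogation process". SAP 7.4 nevertheless expects missing data to have little effect.

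**The concern.** Persistent AF is found by reading the device. A telephone call after the last readout shows that the patient was reachable, not that the patient was free of AF. If follow-up is extended to that call, the patient stays in the risk set for a period in which the event could not be seen.

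The protocol's own procedures can produce such calls. Section 9.10 has the site telephone a patient who misses a visit, and Table 1 allows adverse events to be reported by telephone. In a patient who stays in the study, a later interrogation may recover the stored data. In a lost patient none follows.

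At stake is the accuracy of the descriptive Kaplan-Meier estimates and intervals in SAP 7.9.1, which depend on the censoring date, and whether that date is fixed before the data are seen.

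**Working it through.** **Do the texts settle it?** Preferring the specific rule to the general one does not help: 7.2.2 is specific to the endpoint and 7.4 to the patient. SAP 7.9, 7.9.1 and 7.12 and Protocol 13.2.5 and 13.2.9 set no order. The SAP gives no figure for the effect, so there is none to reproduce.

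**Inputs from the documents.** Control event-free probability of 85% at 24 months, planned loss of 15%, and 37 patients in the smaller arm (all SAP 6).

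**Assumptions.** The hazard is constant. A share f of the arm has device data to month d and a later contact at month c = 18 without interrogation. Everyone else is fully observed to month 18. The documents give neither f nor the gap. I take f from 5% to 15% and d = 12 or 6.

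**Event-free probabilities**, S(t) = 0.85^(t/24):
- S(6) = 0.9602
- S(12) = 0.9220
- S(18) = 0.8852, so the true month-18 incidence is 11.48%

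**Effect of the 7.4 date.** Nobody is censored before month 18, so the Kaplan-Meier estimate is a simple proportion. Affected patients appear event-free whenever they were event-free at d:

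apparent S(18) = (1 − f) S(18) + f S(d), so bias = f [S(d) − S(18)]

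| d to c | f | Month-18 incidence reads | Bias (points) | Events in 37 |
|---|---|---|---|---|
| 12 to 18 | 5% | 11.29% | 0.18 | 0.07 |
| 12 to 18 | 15% | 10.92% | 0.55 | 0.20 |
| 6 to 18 | 5% | 11.10% | 0.37 | 0.14 |
| 6 to 18 | 15% | 10.35% | 1.12 | 0.42 |

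Example: 0.15 × (0.9602 − 0.8852) = 0.0112. In a simulation of 2,000,000 patients with f = 15%, the contact date gave 10.95% (12 to 18) and 10.36% (6 to 18). The save-to-disc date gave 11.50% and 11.49%, so it is unbiased here.

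**Standard error at month 18, n = 37.** With no loss it is √(0.1148 × 0.8852 / 37) = 5.24 points. At f = 15%, Greenwood's formula gives 5.40 (12 to 18) and 5.55 (6 to 18) points under the save-to-disc date, and 5.13 and 5.01 under the contact date.

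**Person-time given up by the save-to-disc date at f = 15%.** For 12 to 18 this is 0.15 × 0.9220 × 6 = 0.83 months per patient out of 16.96, or 4.9%. For 6 to 18 it is 0.15 × 0.9602 × 12 = 1.73 out of 17.01, or 10.2%.

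**Permanent AF.** It is part of the primary endpoint (SAP 4.2.1) but rests on the physician's decision (Protocol 9.6), so it can be declared after the last readout. Suppose such late declarations are counted while event-free patients stop at the device date. In the 6-to-18, f = 15% case the incidence then reads 11.8% if a quarter of the events in the gap are declared permanent AF, and 12.7% if all are, against a true 11.5%. A repair that treats events and non-events differently would reverse the bias.

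**The case against.** The strongest reply is that 7.2.2 already gives the right date for persistent AF and that 7.4 is a general sentence carried over from the protocol. Derivation detail is delegated to the SPR (SAP 7.2.2 and 9.1), and a second programmer or statistician validates the derived datasets (SAP 8). This stands in part. A reader might infer that programmers will diverge, but the documents do not show that: the conflict is unresolved in the SAP and protocol text, and the SPR could resolve it. It would have to override one of two stated rules to do so.

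The affected group is also narrow. In-office visits and remote transmissions both yield device data, so the dates differ only for lost patients with a later contact and no interrogation. Their number is unknown, and the 15% loss is a design input, not a ceiling.

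The SAP has safeguards: "A device data quality analysis will be performed before the derivation of the analysis variables", and 7.12 defers the final decision on evaluating the endpoints. Neither sets a censoring date.

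For burden, the reply is fair. The date-of-notice sentence directly follows the paragraph on adverse-event-derived endpoints and may be meant only for those. Read literally, it also covers the burden times, in any patient with a gap. No size can be given, because the documents provide neither the burden incidence nor the share of patients with a gap.

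**Conclusion.** The point holds as a minor correction. Two stated rules conflict for lost patients. Applied to device-detected persistent AF, the 7.4 rule understates incidence by about 0.2 to 1.1 points at month 18 under the assumptions above. That is at most 0.42 events in 37 patients, with a standard error above 5 points. Whether enough patients reached month 18 before the early termination is not stated.

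Two stronger readings are not supported. One is that the contact date can only lower the primary-endpoint incidence. This is true only for an unchanged set of events: a permanent-AF declaration after the last readout counts under the contact date and is missed under the device date. The other is that the non-inferiority conclusion is at risk. SAP 7.9.1 plans no test and no hazard ratio, and shows curves only if patient and event numbers suffice.

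**What to change.** 1. In SAP 7.4, exempt device-derived endpoints (persistent AF and times to first AT/AF burden). Censor them, in all patients including those lost, at the last date covered by a save-to-disk or remote transmission. Keep contact or visit dates for clinical endpoints, and cross-refer from 7.2.2.
2. Apply that one date to events and non-events alike. A permanent-AF declaration counts in the primary endpoint only if dated on or before it. List later declarations separately.
3. Replace the statement in 7.4 that missing data should matter little with wording that agrees with 7.1.3 and 7.9.
4. Confirm that the SPR uses the same dates.

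The work is a few sentences and one derived date. If 15% are affected, the analysis loses about 5% to 10% of person-time to month 18, and the standard error is about 5.4 to 5.5 points rather than 5.1 to 5.0. Late permanent-AF declarations are left out of the curve.
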